practical part (i.e., microteaching) has been previously identified as essential for applying what has been learned in contexts as close to reality as possible (Aelterman et al., 2013). Ultimately, the adoption of a congruent style, where trainers implement the program using (de)motivating teaching styles has also been positively perceived by PE teachers. This approach allows them to observe real-life examples of how to implement these strategies effectively (Aelterman et al., 2013). Moreover, in line with SDT, it could lead to an immediate effect on the teachers' need satisfaction during the training that has been positively associated with effectiveness and feasibility beliefs in terms of autonomy support and structure, as well as teachers' intentions to apply the proposed strategies (Aelterman et al., 2016).

Finally, while previous studies have considered gender as a covariate to analyze the effects of SDT-based interventions, gender differences in study variables are seldom reported for both teachers and students. Given prior SDT-related research indicating that (de)motivating teaching behaviours may be perceived differently by boys and girls students (White et al., 2021) and male and female teachers (García-Cazorla et al., 2024), it is crucial to determine whether the intervention is equally effective for both genders to mitigate any potential gender-related inequities.

To extend previous knowledge, this mixed-method study describes the protocol of a motivational training program, based on the circumplex model, aimed at improving (de)motivating teaching styles/approaches among PE teachers. The first hypothesis suggests that the features of the motivational training program will be positively perceived by PE teachers (H1). We also hypothesize that experimental school female and male teachers will perceive improvements in several antecedents, autonomy and competence satisfaction/frustration at work, (de)motivating teaching styles/approaches, and (mal)adaptive outcomes at least at the end of the intervention implementation toward students (H2). Finally,

both boys and girls from experimental groups will perceive improvements in their PE teachers' (de)motivating teaching styles/approaches, autonomy and competence satisfaction/frustration in PE, and adaptive outcomes in PE lessons (H3).

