## **Materials and methods**

### ***Context, design, and randomization***

[figure not shown]
This study will be carried out in a northeast region of Spain [details masked for review process]. PE is mandatory for every secondary school student in Spain. Each student receives two 50-minute coeducational PE lessons per week. Spanish Secondary PE teachers are expected to teach between 18 and 21 hours per week. Typically, the annual teaching plan of PE teachers includes approximately six to eight distinct teaching units per year. These units encompass various content types such as individual, cooperative, and interactive sports and games, as well as body expression, health-related fitness, and outdoor activities, all of which are outlined in the PE curriculum. The academic year lasts from September to June, divided into three terms, each separated by a holiday period (i.e., Christmas and Easter).

A randomized controlled trial design with a mixed-method approach will be carried out. PE teachers agreeing to participate in the trial will be randomly assigned to either the experimental or the control group. Randomization will be conducted using the digital tool available at <https://echaloasuerte.com/>. To prevent contamination of the experimental condition, schools will only participate in one group (i.e., experimental or control). Subsequently, at least two groups of students from each PE teacher will be randomly selected.

This study will comprise two phases: 1) a teacher-training phase and 2) an implementation phase with students. It should be noted that the training program will continue with some individual and group sessions during the implementation phase. Since teachers' and students' perceptions of (de)motivating teaching styles and approaches and other study variables require several months for greater accuracy in their perceptions, the

training program will not start until the second term of the academic year (for more details see Figure 1).

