### **Sample size calculation**

The sample size for this intervention-based study was calculated using R Studio to ensure adequate power in the detection of potential statistically significant effects.

Considering a multi-level design nesting center, PE teacher and group, the sample size calculation was grounded on an anticipated effect size of 0.5, reflecting a moderate impact of the intervention. The power of the study was set at 80% with a significance level (alpha) of 0.05, aligning with common practices in educational research (McConnell et al., 2019).

Acknowledging the inherent structure of this study, an Intra-Class Correlation (ICC) of 0.1 was assumed based on similar educational settings (Hedges & Hedberg, 2007). This ICC estimate accounted for the expected homogeneity within the three levels (class group within PE teacher, PE teacher within center). To accommodate potential participant dropout, particularly among students, we incorporated a 40% anticipated dropout rate into our calculations (e.g., Meerits et al., 2022). The minimum sample size was adjusted to 210 students across 15 PE teachers, averaging 14 students per teacher. This adjustment ensures that our study maintains sufficient statistical power even in the face of anticipated losses, thereby safeguarding the integrity and validity of our findings.

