### ***Participants and recruitment***

At least 16 secondary PE teachers, eight in the experimental group and eight in the control group, along with their respective students, will be expected to participate in this study. The maximum number of participating teachers will be capped at 20, due to the limited human resources of the research team. PE teachers will select at least two classroom groups comprising at least 14 students each to invite to participate in this study. Eligible students will be those aged 12 to 17 years in secondary schools. Participation will be voluntary and anonymous.

Various social media platforms (i.e., Instagram, Twitter, and WhatsApp) and other communication methods (i.e., email) will be used for teachers' recruitment. An informative poster will be launched, detailing the target sample, content, aims, and training program dates. This poster will also include two links (QR code): one with a document providing further information and another to registration through a brief Google Forms questionnaire. Regarding the additional information document, it is important to note that it will detail a more comprehensive overview of the objectives, the different phases of the program, inclusion criteria, the requirements that each teacher must accept to participate, and the

teaching skills that will be developed during the training program. Teachers with further inquiries can contact the research team via email or phone. The registration period will last approximately 21 days.

Once the interested PE teachers have registered, various inclusion criteria will be considered for the final selection: 1) Being an in-service PE secondary school teacher for the entire academic year; 2) Attending 100% of the training program sessions; 3) Fill in a short questionnaire at the end of each session of the training program, as well as fulfilling questionnaires of the study variables three times; 4) Allowing the recording of two PE lessons; 5) Participating in two focus groups, one at the end of the training program and one at the end of the study, and 6) Not participating in other training sessions related to PE instruction during the program. Moreover, the inclusion criteria for students will be: 1) Authorization from parents or legal guardians; 2) Completion of questionnaires of the study variables three times; 3) Regular participation in PE lessons.

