### ***Analysis plan***

#### ***Quantitative analyses***

Firstly, the effects of the four sessions of the training program on the study variables assessed in teachers will be examined. The overall mean for each of the 11 variables perceived by PE teachers about the quality of the training program (e.g., interaction, innovation, interest, intelligibility, etc.) will also be calculated, representing the mean across the different sessions. A repeated measures analyses of variance (ANOVA) will be used to assess PE teachers' global appreciation of 11 variables related to the quality of the training program (e.g., interaction, innovation, interest, intelligibility, etc.) across the sessions of the training (i.e. within-subject analyses). Accordingly, each of the training sessions will be introduced as an independent variable (i.e. within-subject factor) and repeated measures of the PE teachers-related variables will be entered sequentially as dependent variables.

Secondly, the effects of the intervention implementation in PE lessons on study variables for both teachers and students will also be examined. Levene and Kolmogorov–Smirnov tests will be used to ensure the equality of variances and normal data distribution, respectively ( $p > .05$ ). Cronbach's coefficient will be calculated for each study variable across the three measurements. To examine the effects of the intervention on study variables, a  $3 \times 2$  (time x condition) repeated measures multivariate analysis of covariance (MANCOVA) will be performed for both teachers and students. Age, gender, teaching experience, type of school (public or private), and school location (rural or urban) will be introduced as covariates among teachers, while age, gender, and school grade level will be introduced as covariates among students. Subsequently, to examine intragender differences of the intervention on study variables, a  $3 \times 2 \times 2$  (time x condition x gender) repeated measures MANCOVA will be performed for both teachers and students. The same covariates will be entered as previously analysis, excluding gender. Multiple paired t-tests with Bonferroni correction will be calculated to determine between-group (i.e., experimental-control group) and within-group (i.e., pre-post) differences. Cohen's criteria will be used as indicators of small (.01), moderate

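### Paired t-tests are specified for the experimental-control comparison although the arms are independent and clustered, and within-arm pre-post tests stand beside it with no rule for reading them

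*Protocol*

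**What the plan says.** Under Quantitative analyses, the protocol examines intervention effects with a 3 × 2 analysis: "time x condition) repeated measures multivariate analysis of covariance (MANCOVA) will be performed for both teachers and students". A version with gender added follows. The follow-up tests are then fixed in one sentence: "Multiple paired t-tests with Bonferroni correction will be calculated to determine between-group (i.e., experimental-control group) and within-group (i.e., pre-post) differences".

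The design is set out under Context, design, and randomization: "PE teachers agreeing to participate in the trial will be randomly assigned to either the experimental or the control group", and "schools will only participate in one group (i.e., experimental or control". Participants and recruitment gives the minimum size: "At least 16 secondary PE teachers, eight in the experimental group and eight in the control group". No matching or pairing of teachers, schools, classes or students across arms appears anywhere.

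The hypotheses at the end of the Introduction are worded as change in the experimental group. H3, for example, expects that "both boys and girls from experimental groups will perceive improvements". H2 is worded in the same way for teachers. Neither names the control group as comparator.

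**The concern.** A paired t-test works on differences within a natural pair. The pre-post comparison has such pairs, because each person is measured more than once. The experimental-control comparison has none: the arms contain different teachers, different schools and different students. As written, the test that is meant to locate the difference between arms is undefined.

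Two further problems sit in the same sentence. First, a t-test on students treats them as independent, although teachers are randomised and the protocol itself assumes an ICC of 0.1. Second, pre-post tests within each arm are listed on an equal footing with the between-arm test. Perceptions can change over a school year without any program. Because H2 and H3 speak only of improvement in the experimental group, a significant pre-post change there could be taken as support for them even if the control group changed by the same amount.

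**Working it through.** **1. The protocol's own sample size implies independent groups.** Inputs from Sample size calculation: "the sample size calculation was grounded on an anticipated effect size of 0.5"; "The power of the study was set at 80% with a significance level (alpha) of 0.05" (two-sided assumed); 40% dropout.

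- n per arm = 2(1.960 + 0.842)² / 0.5² = 62.8, so 63 per arm and 126 in total.
- 126 / (1 − 0.40) = 210, the stated minimum.

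This is the formula for two independent samples, which does not fit a paired between-arm test. (It reproduces 210 only with no design effect. That is a separate matter.)

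**2. What the mispairing does by itself.**

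- Unequal arms: the test cannot be computed. With 40% dropout expected among students, equal arms are unlikely.
- Equal arms: the p-value depends on row order. In one simulated 8 v 8 data set the independent t-test gave p = 0.061. Across 20,000 random re-pairings of the same data, the paired p ranged from 0.0008 to 0.168.
- Power: with 8 v 8 teachers, the degrees of freedom fall from 14 (critical t 2.145) to 7 (2.365). At a standardised difference of 1.0, power falls from 46.1% to 40.8%. With 63 v 63 students at 0.5, clustering ignored, it falls from 79.5% to 78.9%.
- Type I error: not inflated when there is no clustering (see step 3).

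**3. What ignoring the clustering does.** Inputs: 8 teachers per arm; ICC 0.1; 14 students per teacher (the average in Sample size calculation) or 28 (two classes of at least 14, from Participants and recruitment). Simulated rejection rates with no true effect at nominal 5%, over repeated runs:

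| ICC | Students per teacher | Arbitrarily paired | Independent |
|---|---|---|---|
| 0.1 | 28 | 28–31% | 29–32% |
| 0.1 | 14 | 19–21% | 20% |
| 0 | 28 | about 5% | about 5% |
| 0 | 14 | about 5% | about 5% |

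A closed-form check agrees. The design effect is 1 + (m − 1) × 0.1, which is 3.7 for m = 28 and 2.3 for m = 14. The true error is about 2Φ(−1.96/√3.7) = 30.8% and 2Φ(−1.96/√2.3) = 19.6%. All the inflation comes from clustering and none from the pairing.

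**4. What the within-arm tests can show.** Assumptions, none given in the protocol: both arms drift 0.2 SD in the improving direction, there is no program effect, and the pre-post correlation r is 0.5 to 0.7. There are 63 completers per arm (126/2, from step 1), and clustering is ignored. Noncentrality = 0.2 × √63 / √(2(1 − r)).

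| r | Noncentrality | Significant at 0.05 | Significant at 0.05/3 |
|---|---|---|---|
| 0.5 | 1.59 | 35% | 20% |
| 0.7 | 2.05 | 52% | 35% |

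The protocol does not define the Bonferroni family. The last column assumes three time-pair comparisons.

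A stricter count asks how often only the experimental arm is significant when both arms share the same true change. For p the chance of significance in one arm, this is p(1 − p). Over assumed drifts of 0.1 to 0.3 SD and r of 0.3 to 0.7, it is 9–25% with 63 per arm and 5–13% with 8 per arm, unadjusted.

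**The case against.** The strongest reply is that the sentence is a slip. Bonferroni-corrected pairwise comparisons are a usual follow-up to a repeated-measures model, and software would refuse a paired test on unequal arms, so the error may correct itself. That may well be the intent. But the protocol fixes a named test, and a pre-specified procedure that must be replaced at analysis no longer constrains the analyst.

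A second reply is that the time-by-condition MANCOVA is the stated analysis of intervention effects. This stands, and it limits the point. A reader might infer that the protocol offers the pre-post tests as evidence of effect, or that they decide H2 and H3. The text does not say so. It says only that the t-tests determine differences, and the hypotheses are directional expectations in an introduction. What remains is that nothing says how a pre-post result is to be read against the between-arm result, while the hypothesis wording invites the wrong reading.

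A third reply is that the inflated type I error has nothing to do with pairing and applies equally to a MANCOVA without a teacher term. This is correct. A reader might infer that the wrong pairing produces the 20–31%, and the ICC 0 rows rule that out. The figures matter here only because they show that switching to an ordinary independent t-test would not repair the student comparison.

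**Conclusion.** The point holds for the follow-up tests. The between-arm test is invalid as written: it has no pairs, it cannot be run with unequal arms, and with equal arms its result is arbitrary. The direct statistical cost of the mispairing is small, a modest loss of power.

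The larger error comes from any student-level t-test that ignores the teacher-level randomisation: about 28–31% type I error with 28 students per teacher and about 20% with 14, given the protocol's ICC of 0.1 and eight teachers per arm.

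Within-arm tests cannot demonstrate a program effect. The 35–52% (unadjusted) and 20–35% (three comparisons) rest on an assumed 0.2 SD drift, an assumed correlation of 0.5–0.7 and 63 completers per arm. They illustrate the risk and do not forecast it. The documents do not support a claim that the trial's main effect analysis is a paired or within-arm test.

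**What to change.** - Delete the paired t-tests for between-group differences.
- For student outcomes, estimate experimental-minus-control contrasts at T2 and T3, adjusted for the T1 score, from a model with random effects for teacher/school and class and small-sample degrees of freedom.
- For teacher outcomes, use an independent-groups contrast adjusted for T1.
- Apply the Bonferroni correction to these between-arm contrasts over a stated family that takes account of the number of outcomes as well as the two time points.
- Keep paired pre-post changes as description only.
- State that H2 and H3 are judged on the between-arm contrast.

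The cost is analysis wording and model code. No new data or recruitment is needed. P-values will be less favourable, because the clustering is respected.

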## Introduction

Physical Education (PE) teachers hold a pivotal role in guiding students through their learning process. Drawing on Self-Determination Theory (SDT; Ryan & Deci, 2020), teachers' (de)motivating style, referred to as "the interpersonal sentiment and behaviour that teachers rely on during instruction to motivate students to engage in and benefit from learning activities" (Reeve et al., 2014, p. 94), is a crucial element in the teaching process. Recent research suggests that PE teachers employ a diverse array of teaching behaviours in their educational practice (Burgueño, García-González, et al., 2024). Autonomy, competence, and relatedness-supportive teaching behaviours (i.e., need-supportive teaching behaviours) have been positively related to students' autonomous motivation and adaptive outcomes in PE, while the opposite is true for autonomy, competence, and relatedness-thwarting behaviours (i.e. need-thwarting behaviours) (Vasconcellos et al., 2020; White et al., 2021). Consequently, continuous development teaching (CDT) programs, based on SDT (Ryan & Deci, 2017), has increased in the last years. These SDT-training programs, mainly focused on autonomy-supportive strategies, revealed positive effects on students' perceptions of (de)motivating teaching behaviours and motivational outcomes (Vasconcellos et al., 2020). Over the past decade, SDT-training programs have also demonstrated positive effects on teachers' self-perceptions of certain antecedents, support for autonomy and structure, and various motivational and (mal)adaptive outcomes (Reeve & Cheon, 2021). However, additional research is required, as most studies have not focused on reducing need-thwarting behaviours.

Recently, grounded in SDT (Ryan & Deci, 2017), the circumplex model (Aelterman et al., 2019) offers a detailed view of the different (de)motivating teaching styles (i.e., autonomy support, structure, control, and chaos) that teachers can adopt in their classes. This circumplex model delineates eight teaching approaches across these four teaching styles (Aelterman et al., 2019; Escrivá-Boulley et al., 2021). To develop the most effective

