(.06), and large (.14) effect sizes (Field, 2017). All statistical analyses will be conducted using IBM SPSS Statistics v.25.0. Finally, a longitudinal structural equation model will be used to analyze the predictive relationships between the study variables, allowing for observation of potential differences at the three specific times (i.e., pre-test, middle, and post-test) when data are collected.

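### With 16 to 20 teachers, the .01/.06/.14 effect-size labels often call a null teacher effect moderate or large

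*Protocol*

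**What the plan says.** The Quantitative analyses section fixes the cut-offs in one sentence: "criteria will be used as indicators of small (.01), moderate", continuing with "06), and large (.14) effect sizes (Field, 2017". The sentence names no index and is not limited to significant effects or to particular tests. It gives no confidence interval and no bias correction.

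The same section says that a 3 x 2 ("time x condition) repeated measures multivariate analysis of covariance (MANCOVA) will be performed for both teachers and students"). For teachers there are five covariates: "Age, gender, teaching experience, type of school (public or private), and school location (rural or urban) will be introduced as covariates among teachers". A second model adds gender as a factor, and for it the plan says "The same covariates will be entered as previously analysis, excluding gender".

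Participants and recruitment sets the number of teachers: "At least 16 secondary PE teachers, eight in the experimental group and eight in the control group", and "The maximum number of participating teachers will be capped at 20".

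On the number of outcomes, the Introduction says "This circumplex model delineates eight teaching approaches across these four teaching styles". The Measures section adds four need scales, job satisfaction, emotional exhaustion and job performance. That gives 4 + 4 + 3 = 11 teacher outcomes if styles are analysed, or 8 + 4 + 3 = 15 if approaches are.

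**The concern.** Partial eta-squared is a share of sample variation. It cannot be negative, so it is above zero on average even when there is no effect, and the excess grows as error degrees of freedom fall. Fixed cut-offs are harmless in a large sample. In a sample of 16 to 20 with five covariates, the expected value under no effect may itself reach the moderate band.

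What is at stake is how the teacher results are described. If chance alone often earns a moderate or large label, the label tells the reader little about what the programme did for teachers. Results could also be reported as large when their own p-value does not separate them from zero.

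**Working it through.** The protocol gives no figure for how the labels behave, so there is none to reproduce.

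**Assumptions.** The index is (partial) eta-squared, errors are normal and spherical, each covariate costs one degree of freedom, and all teachers have complete data.

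**Univariate time x condition.** Let v = N − 2 − (number of covariates). The test has 2 and 2v degrees of freedom. Under no effect the index follows Beta(1, v), so:

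- mean = 1/(1 + v)
- P(above c) = (1 − c)^v
- value needed for p = .05: 1 − .05^(1/v)

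| N | Covariates | v | Null mean | At least moderate (.94^v) | Large (.86^v) | Needed for p = .05 |
|---|---|---|---|---|---|---|
| 16 | 5 | 9 | 0.100 | 57% | 26% | .28 |
| 18 | 5 | 11 | 0.083 | 51% | 19% | .24 |
| 20 | 5 | 13 | 0.071 | 45% | 14% | .21 |
| 16 | 0 | 14 | 0.067 | 42% | 12% | .19 |
| 20 | 0 | 18 | 0.053 | 33% | 7% | .15 |

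Under no effect 5% of tests are significant, and all of those exceed .14. With covariates, the share of null tests that are labelled large while non-significant is therefore about 26 − 5 = 21% at N = 16 and 14 − 5 = 9% at N = 20.

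**Time x condition x gender, four covariates.** Four cells and four covariates give v = N − 8. At least moderate: .94^8 = 61% (N = 16) and .94^12 = 48% (N = 20). Large: .86^8 = 30% and .86^12 = 16%.

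**Session-quality repeated measures ANOVA**, if the cut-offs are meant to cover it. With 8 to 10 experimental teachers and four sessions the degrees of freedom are 3 and 21 to 3 and 27. Under the null, 72% to 64% are at least moderate and 36% to 25% are large.

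**Multivariate time x condition, five covariates.** The protocol states neither the form of the test nor how outcomes are grouped, so the result is a range.

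- Averaged repeated-measures form (hypothesis df 2, error df 2(N − 7); Pillai's trace divided by 2, simulated under the null). With four outcomes, 74% (N = 16) and 47% (N = 20) are large. With eight, 99.7% and 97.5%. With 11 or 15, at least 99.9%. With only two outcomes, 70% and 53% are at least moderate.
- Doubly multivariate form (2q contrasts for q outcomes, error df N − 7). The index follows Beta(q, (N − 7 − 2q + 1)/2). With two outcomes this is Beta(2, 3) at N = 16 and Beta(2, 5) at N = 20, so 90% and 80% are large. With four outcomes at least 99.5% are large. With eight or more the test cannot be computed, because 16 contrasts exceed the 9 to 13 error degrees of freedom.

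**The case against.** Several points on the other side are sound.

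- **A reader might infer that the teacher hypothesis (H2) will be decided by the labels.** The protocol does not say so. It plans MANCOVA tests and Bonferroni-corrected comparisons, sets alpha at .05, and calls the cut-offs indicators. Eta-squared also has no sign, while H2 predicts improvement, so a large label under the null reflects worsening as often as benefit.
- **A reader might infer that the cut-offs clash with the planning effect size of 0.5.** They do not. Read as a standardised mean difference with equal groups, 0.5 converts to 0.5²/(0.5² + 4) = 0.25/4.25 = .059, which is almost exactly the moderate cut-off.
- **A reader might infer that the fault is confined to teachers.** That is not established. With 210 students treated as independent, a null univariate effect practically never passes .06, but that ignores clustering within classes and teachers. Even on that footing, in the doubly multivariate form with 15 outcomes about half of null results pass .14.
- **The covariates contribute much of the bias.** Without them the null mean drops to 1/17 = 0.059 at N = 18 and 0.053 at N = 20, just under the moderate cut-off. Even so, 33% of null tests at N = 20 are labelled at least moderate, and the protocol does plan the covariates.
- **Small N is the root cause, and a better index does not remove it.** Partial epsilon-squared at N = 16 with covariates still passes .06 in 22% and .14 in 10% of null tests. Hedges' g at 8 versus 8 exceeds 0.5 in absolute value in 31%. This is why the remedy needs intervals as well as a different index.
- **The index is inferred, and an unseen analysis plan might name it and add intervals.** The inference is reasonable but remains an assumption. The cut-offs themselves are fixed in the protocol, so the rule can be judged as it stands.

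**Conclusion.** The point holds as a fault in a stated interpretive rule. If the index is (partial) eta-squared, the .01/.06/.14 labels are not valid indicators of effect size in the teacher analyses.

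For the planned covariate-adjusted univariate test, a true null earns at least a moderate label about half the time (57% to 45%) and a large label in 26% to 14% of tests. For the multivariate tests the size of the problem cannot be given as one number, because the form and grouping are unstated. It is severe in every case worked with four or more outcomes, and near certainty in the averaged form with eight or more.

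The conclusion does not extend to a claim that H2 would be accepted on labels alone. It concerns how teacher effects are described and does not affect the significance tests. It rests on the normality, sphericity and complete-data assumptions given with the calculation.

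**What to change.** State in the Quantitative analyses section that the .01/.06/.14 labels are not applied to teacher results. Report adjusted mean differences with 95% confidence intervals, adding Hedges' g if a standardised measure is wanted. If a variance-explained index is preferred, use partial epsilon-squared or omega-squared with confidence intervals. Either way, interpret size from the interval and put no label on the point estimate.

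Name the index wherever one is reported, and state the form of the multivariate test and how outcomes are grouped, so that any multivariate effect size can be read properly.

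The cost is analysis wording only: design, sample size and data collection stay as they are. Teacher effects will look smaller and less certain. With 16 to 20 teachers the intervals will be wide, and the change does not cure the small sample.
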